3.10.3 Methods for assessing and recording of AEs / SAEs

The study protocol will be halted at any moment of the study period if the study participants develop any sudden (expected or unexpected) severe complications / adverse events. The withdrawal of a study participant from the trial will be documented on the adverse event page of the CRF and the participant will be further followed up for the study outcomes and included in the analysis as per the original randomization group (intention-to-treat analysis). All AEs / SAEs will be recorded and graded according to the Common Terminology Criteria for Adverse Events (CTCAE) version 5 and US FDA's Toxicity Grading Scale Healthy Adults and Adolescents Volunteers Enrolled in Preventive Vaccine Clinical Trials criteria as shown in Appendix III and IV.^{42,43}

3.10.4 Local skin reaction

Prior to the IV cannulation and after blood transfusion, the adhesive dressing will be removed and skin antisepsis will be performed. The investigator will visually examine the tested site for any evidence of skin irritation. Photos will be taken for further documentation. Among local AEs / SAEs that will be solicited and documented are as follows:

- Pain
- Erythema (redness)

- Ecchymosis (bruising)
- Swelling
- Pruritus (itchiness)
- Tenderness (pain upon touching the cannulation site)

The patients will be followed up via phone call within 24 hrs after the procedure to obtain any subsequent evidence or occurrence of skin irritation. Any local skin reaction will be described and documented in terms of its maximum intensity, duration of reaction, subsequent action taken to mitigate any adverse event, potential causal link with the study intervention / control and the evolution of the skin reaction: (1) continues; 2) recovered with sequel; 3) recovered without sequel; 4) unknown.

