3.10.6 Reporting of AEs / SAEs to the Institution Review Board (IRB)

All AEs will be recorded in the CRFs. AEs of grade 3 and above will be reported to the UKM Human Ethics Committee within 5 business days. All SAEs (including Serious Unexpected Suspected Adverse Events (SUSARs)) will be reported within 24 hours of occurrence (expedited reporting), to the UKM Human Ethics Committee. The reporting procedures for SAEs should adhere to the following steps:

- i) The SAEs initial report form should be filled in by the assessors (medical officers) and reviewed and signed by the PI ([name] [name]) or the co-investigator ([name]).
- ii) The SAEs initial report should then be submitted to the UKM Ethics Committee in an expedited fashion.
- iii) SAEs should be reviewed and followed to resolution by the medical officers / PI / co-investigator in charge of study participant
- iv) A subsequent follow-up report will be submitted that documents any additional important information, including the resolution of SAEs.

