3.10.7 Study Halting Criteria

Participant enrolment and allocation and institution of interventions will be stopped if one of the following occur:

- a) Death related to microneedle or EMLA application
- b) Any participant experiences bronchospasm, laryngospasm or anaphylaxis within 24 hours post microneedle or EMLA application
- c) Any SAE related to microneedle or EMLA application
- d) Any AE of grade 3 and above or any SAE that cannot obviously be implicated on other causes
- e) Any study participant who develops abscess / ulceration / erosion at the site(s) of microneedle or EMLA application

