APPENDIX III

| LOCAL SKIN REACTIONS | GRADES | | | | |
|----------------------|---------|--|---|--|--|
| | 0 (Nil) | 1 (Mild) | 2 (Moderate) | 3 (Severe) | 4 (Life Threatening) |
| Pain | Nil | Does not interfere with activity | Repeated use of non-narcotic pain reliever for more than 24 hours or interferes with activity | Any use of narcotic pain reliever or prevents daily activity | Emergency room (ER) visit or hospitalization |
| Erythema | Nil | 2.5 cm – 5 cm | 5.1 cm – 10 cm | >10 cm | Necrosis or exfoliative dermatitis |
| Ecchymosis | Nil | 2.5 cm – 5 cm | 5.1 cm – 10 cm | > 10 cm | ER visit or hospitalization |
| Swelling | Nil | 2.5 cm – 5 cm and does not interfere with activity | 5.1 cm – 10 cm or interferes with activity | >10 cm or prevents daily activity | Necrosis |
| Pruritus | Nil | Mild or localized, requires topical intervention | Widespread and intermittent, limiting instrumental activity of daily living (ADL), requires oral intervention | Widespread and constant, limiting self-care ADL, requires systemic corticosteroid or immunosuppressive therapy | - |
| Tenderness | Nil | Mild discomfort to touch | Discomfort with movement | Significant discomfort at rest | ER visit or hospitalization |

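### Active safety solicitation ends with one phone call within 24 hours, so later-onset abscess, ulceration or erosion (halting criterion (e)) and the analgesic route to grade 2 pain depend on unsolicited reports

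*Combined protocol and SAP*

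**What the plan says.** All of this is in the combined protocol and SAP.

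- **On the day (3.10.4).** Before cannulation and after transfusion, "The investigator will visually examine the tested site for any evidence of skin irritation", and photographs are taken.
- **After the visit (3.10.4).** "The patients will be followed up via phone call within 24 hrs after the procedure", the purpose being "to obtain any subsequent evidence or occurrence of skin irritation". Section 3.10.5 uses a similar scheme for systemic reactions.
- **What is recorded (3.10.4).** Maximum intensity, duration, action taken, causal link and "the evolution of the skin reaction: (1) continues; 2) recovered with sequel; 3) recovered without sequel; 4) unknown".
- **What is solicited (3.10.4).** Pain, erythema, ecchymosis, swelling, pruritus and tenderness, introduced as being among the reactions sought.
- **Halting (3.10.7).** Criterion (e) reads "Any study participant who develops abscess / ulceration / erosion at the site(s) of microneedle or EMLA application". It carries no time limit. Criterion (b) does: "Any participant experiences bronchospasm, laryngospasm or anaphylaxis within 24 hours post microneedle or EMLA application".
- **Grading (Appendix III).** Grade 2 pain is "Repeated use of non-narcotic pain reliever for more than 24 hours or interferes with activity". The table has no row for abscess, ulceration or erosion.
- **Events already reported (3.10.3, 3.10.6, 3.10.8).** All AEs go into the CRF with no stated closing time. SAEs are followed to resolution. Severe events can halt the protocol at any time in the study period. AEs or SAEs that occur or are ongoing at the end of the study are followed until they resolve, unless the principal investigator judges this unnecessary.
- **Next contact (3.9.2).** The next intervention follows a washout of at least three weeks.

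**The concern.** A halting rule works only if the events that trigger it come to light. Under criterion (e), a single abscess, ulceration or erosion at an application site stops enrolment and further interventions. No time limit is attached, so an event appearing days after the visit counts as much as one on the day. Yet the last scheduled enquiry falls no later than 24 hours after the procedure, is made by phone, and asks about skin irritation in general terms. The three events are not named in what the investigator solicits or in the table used for grading.

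The grading table has a smaller version of the same problem: part of its pain scale needs observation for longer than the call allows.

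This is a phase II trial of a microneedle prototype that breaches children's skin. If a family does not volunteer a late site reaction, it is not counted, criterion (e) is not triggered, and applications continue. The published safety summary would then describe mainly the first day, although nothing in the plan limits it to that day.

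**Working it through.** The plan gives no figure for this point, so there is none to reproduce. The check compares the timing rules and counts the applications they affect.

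**Step 1. Timing of detection against what the rules need**

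| Rule | Time it needs | Scheduled look that could meet it |
|---|---|---|
| Criterion (e), onset on the day of the visit | Same day | Yes: post-transfusion inspection, then the call |
| Criterion (e), later onset | No limit stated | None after the call, in the visible text |
| Grade 2 pain, interference with activity | Any time | Yes: can be reported at the call |
| Grade 2 pain, pain-reliever use | More than 24 h | None: the call is at 24 h or earlier |
| Duration and evolution of a reaction still present at the call | Until it resolves | No scheduled contact; it can be coded as continuing |

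The minimum interval to the next application is 3 × 7 × 24 = 504 h. The call comes at or before 24 h, so at least 504 − 24 = 480 h pass with no scheduled safety contact. The two clocks start within the same visit, so the result is approximate by a few hours. Even at the next visit, the text schedules no inspection of the earlier site and no questions about the interval.

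**Step 2. Applications affected**

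- Participants: 26 (3.12). Periods: 4 (Table 1).
- Applications: 26 × 4 = 104, a maximum before drop-out. With the 23 participants in 3.12 before the attrition allowance, it would be 23 × 4 = 92.
- Followed by another study visit: 26 × 3 = 78.
- Not followed by any study visit described in the text: 26 of 104, or 25%.

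**Step 3. How many of the last applications involve the microneedle**

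In Table 1, 6 of the 24 sequences end in D, the control (ABCD, ACBD, BACD, BCAD, CABD, CBAD). The other 18 end in a microneedle arm. If sequences are equally likely, the expected number of last applications with a microneedle is 26 × 18/24 = 19.5.

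**Step 4. Naming of the events**

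The six solicited local reactions in 3.10.4 match the six rows of Appendix III. None is abscess, ulceration or erosion. The nearest entries are necrosis at grade 4 in the erythema and swelling rows, and necrosis or exfoliative dermatitis is not the same as an abscess or an erosion. The list, the table and criterion (e) therefore do not line up.

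**The case against.** The strongest reply is that safety collection stays open after the call, and this is correct. A reader might infer that it closes at 24 hours. The documents do not say so: 3.10.3, 3.10.6 and 3.10.8 keep recording, halting and follow-up open, and a late lesion that a family reports would be recorded and would trigger criterion (e). Section 3.10.8 also covers events that occur at the end of the study, so it is not confined to events already known. What ends at the call is scheduled enquiry. The open provisions act on events that someone has reported, and none of them schedules detection.

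Other parts of the reply also stand:

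- Criterion (e) is not wholly out of reach. An early erosion or ulceration can be seen at the post-transfusion inspection or mentioned in the call. The documents give no onset times, so how many such events would come late is unknown.
- Grade 2 pain is not out of reach either. Interference with activity is enough and can be heard at the call. Only the pain-reliever route is affected.
- The solicited list is not presented as exhaustive, and pain, swelling or tenderness could lead to a lesion being found. Section 3.10.3 also cites CTCAE version 5, which may offer grades that Appendix III does not show.
- Dividing 24 hours by the three-week interval gives a share of calendar time, not of expected events, so it does not measure under-counting.
- A reader might add that the call can precede the end of the 24-hour window in criterion (b). That leaves at most a few hours, for acute events unlikely to depend on a scheduled call to become known. It is not part of this point.
- Figure 5, which shows the visit flow, is not available, and consent pages that might tell families what to report were removed.

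None of this supplies a scheduled look in the visible text after 24 hours.

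**Conclusion.** The point holds in a limited form. Followed as written, the plan has no scheduled means of detecting a criterion (e) event that begins after the call, or of confirming pain-reliever use beyond 24 hours. Both depend on families volunteering the information. The gap applies to each of up to 104 applications. It is widest for the last 26, about 19.5 of them expected to involve the microneedle, because no later study visit is described.

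The number of events that would be missed cannot be estimated from the documents, and it may be small. The conclusion assumes that Figure 5 adds no later contact or site check, and that end of study in 3.10.8 (not defined as per participant or whole trial) does not imply one. It does not support a claim that late events are excluded from the record or that the halting rule cannot operate. This is a worthwhile, inexpensive improvement to the safety plan and does not affect the efficacy analysis.

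A separate and minor wording point: 3.10.6 runs the 24-hour SAE reporting clock from occurrence, which cannot be met for an event the site learns of later. The authors should say whether awareness is meant.

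**What to change.** Keep the call within 24 hours. It is the only scheduled contact on the first day after the visit, and moving it later would give that up.

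In 3.10.4, add:

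1. Before the patch is applied at each later visit, an inspection of the previous application site against the stored photographs, with scripted questions about the interval: pain-reliever use and its duration, discharge, and open skin.
2. The same inspection and questions at the next routine transfusion after the fourth application.
3. Abscess, ulceration and erosion in the solicited list, with corresponding rows in Appendix III, so that the list, the grading table and criterion (e) in 3.10.7 are reconciled. The grade boundaries are for the investigators to set.

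If Figure 5 already shows such a check, it is enough to state it in 3.10.4.

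**Cost.** Protocol and CRF wording and a few minutes at transfusion visits the children already attend. Safety follow-up after the last application lengthens to the next transfusion, recall over the interval will be imperfect, and there is slightly more CRF work. Endpoints, sample size and the halting criteria are unchanged.

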The investigator identified and drew a grid of 1cm × 1cm at the dorsum hand, which served as an ideal site for cannulation. The administrator of intervention (procedurist) will apply either 1 FTU of EMLA Cream (approximately 0.68 g/cm²) or 0.5 FTU (approximately 0.369 g/cm²) over the preparation area. If the patient is subjected to MN patching at his/her visit, the MN patch will be applied by thumb force and pressed firmly against the hand surface for 5 seconds to patch MN to the skin entirely before applying EMLA cream. Otherwise, an empty (i.e. without MN) PVA-containing PET sham patch will be applied instead. Besides, the height-to-base ratio (4:1) used for MN will also optimally minimise its adverse effects (pain, redness), thus preserving the masking (blinding) of study participants from knowing the types of interventions received. The preparation area will be covered with an adhesive dressing (Tegaderm™; 3M, Maplewood, Minnesota, USA) after EMLA cream application. After the allocated application time (15 or 30 minutes), the attending medical officer will set up the transfusion line with a 22-gauge hypodermic needle inserted into the dorsum hand. Throughout the process, the parents/guardians will be allowed to stay by the patient's side at all times.

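### Local skin reactions are recorded by maximum intensity with no time point at a site that is also cannulated, so the recorded grade can mix cannula and microneedle/EMLA effects

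*Combined protocol and SAP*

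**What the plan says.** **One site.** In section 3.9.2 the investigator "drew a grid of 1cm × 1cm at the dorsum hand, which served as an ideal site for cannulation". The microneedle or sham patch and then the cream go on that area. After 15 or 30 minutes "the attending medical officer will set up the transfusion line with a 22-gauge hypodermic needle inserted into the dorsum hand".

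**Inspections on both sides of the puncture.** Section 3.10.4 states: "Prior to the IV cannulation and after blood transfusion, the adhesive dressing will be removed and skin antisepsis will be performed". It continues: "The investigator will visually examine the tested site for any evidence of skin irritation". Photographs are taken, with no time point given, and a phone call follows within 24 hours.

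**Signs solicited.** These are pain, erythema, ecchymosis, swelling, pruritus and tenderness. Tenderness is worded around the cannula itself: "Tenderness (pain upon touching the cannulation site".

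**How a reaction is recorded.** "Any local skin reaction will be described and documented in terms of its maximum intensity, duration of reaction", followed by action taken, "potential causal link with the study intervention / control and the evolution of the skin reaction". No grade per inspection is asked for. The causality scale in 3.10.2 asks about a link with the microneedle or EMLA and allows for an alternative factor. Its only example of one is the patient's disease or clinical state.

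**Analysis.** Section 3.14 plans no analysis of local reactions.

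**The concern.** Bruising, swelling and tenderness can follow any cannulation, and all four interventions end in one. Once the needle is in, a sign at the marked area may come from the patch, the cream, the cannula or the transfusion. Only the pre-cannulation look is free of cannula effects, and the text does not require its grade to be kept as a separate entry. If a single maximum is recorded per visit, a later cannula bruise can set it.

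The causality entry does not clearly rescue this. Under section 3.8 outcome assessors are blinded, and every visit includes EMLA, so a temporal relationship to study treatment is always present. What would help an assessor separate patch from needle is whether the sign was there before the needle went in, and that is what may go ungraded.

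At stake is how readable the local tolerability data are for a prototype microneedle in a phase II paediatric trial. A pre-cannulation finding that is not graded at the visit may not be recoverable later.

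**Working it through.** The plan states no figure on this point, so there is none to reproduce. The textual check comes first, then an illustration of size.

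**Text side by side**
- Treated site and cannulated site: the same 1 cm × 1 cm area (3.9.2).
- Observation times: before cannulation, after transfusion, and a phone call (3.10.4).
- Intensity recorded: a maximum, with no time attached (3.10.4).
- Causes offered: study intervention or control (3.10.4); microneedle or EMLA, or an unspecified alternative factor (3.10.2). Cannulation is not named.

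A cannula effect can therefore supply the recorded grade, and nothing in the text requires the earlier grade to be kept beside it.

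**Illustration: inputs**
- n = 26 (section 3.12).
- m = 0.30, the probability of a device reaction at a microneedle visit, with 0 at the sham visit. Assumed.
- b = 0.20, 0.30 or 0.50, the probability that a cannulation leaves a reaction. Assumed; the documents give no rate.
- Outcome: any local reaction at the visit. Test: exact two-sided McNemar at 0.05, one microneedle visit against the sham visit. Neither the composite nor the test is in the plan.

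**Visible difference**
- Microneedle visit: 1 − (1 − b)(1 − m). Sham visit: b. Difference: m(1 − b).
- b = 0: 0.30
- b = 0.20: 0.30 × 0.80 = 0.24
- b = 0.30: 0.30 × 0.70 = 0.21
- b = 0.50: 0.30 × 0.50 = 0.15

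The sham rate rises from 0 to b and the microneedle rate from 0.30 to 0.44, 0.51 or 0.65, so absolute rates are inflated while the contrast shrinks. It reaches zero only if b = 1.

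**Power.** The result depends on how far cannula reactions recur in the same child, so two extremes are shown.
- *Independent between visits:* discordant probabilities are p10 = [1 − (1 − b)(1 − m)](1 − b) and p01 = b(1 − b)(1 − m). At b = 0.20 these are 0.44 × 0.80 = 0.352 and 0.20 × 0.56 = 0.112.
- *Fully shared within child:* p10 = m(1 − b) and p01 = 0. All discordant pairs then point the same way, and significance needs at least 6 of them, since 2 × 0.5^6 = 0.031 but 2 × 0.5^5 = 0.063. Power is P(Binomial(26, m(1 − b)) ≥ 6).

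| b | Difference | Power, independent | Power, shared |
|---|---|---|---|
| 0 (pre-cannulation reading alone) | 0.30 | 0.84 | 0.84 |
| 0.20 | 0.24 | 0.33 | 0.62 |
| 0.30 | 0.21 | 0.23 | 0.47 |
| 0.50 | 0.15 | 0.12 | 0.19 |

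If the device reaction rate is only 10%, power at n = 26 is about 0.05 or less with or without separation, so the gain from separate recording would not show up in a test.

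**The case against.** **The maximum is per reaction, not stated to be across inspections.** This stands. Taking the maximum over both inspections is a fair reading, but it is an inference. Redness seen before the needle and a bruise seen after it are also different listed signs and could be entered separately. The case report form is not among the documents and may already have a column per time point.

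**Existing safeguards.** These stand in part. There is a look before the needle, there are photographs, and a causal link is recorded. The causality scale's example of an alternative factor is not exhaustive, so an assessor could cite cannulation. Each child's sham visit carries the same cannulation. Patch pain is scored on its own: section 3.9.3 takes a VAS one minute after the microneedle or sham patch, before the cream.

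**A reader might infer that the rule hides every microneedle reaction.** The documents do not support that. Given these safeguards, and since the visible difference is m(1 − b), the effect is dilution.

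**A reader might infer that cannula bruises would set off the halting or expedited reporting rules.** The documents do not support that for ordinary bruises. Ethics reporting of AEs starts at grade 3 (3.10.6). Among the halting criteria (3.10.7), the one based on grade also starts at grade 3 and exempts events obviously due to another cause. Appendix III puts grade 3 ecchymosis above 10 cm.

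**A reader might infer that only the pre-cannulation reading can show a device reaction.** This is also too strong: a delayed reaction would appear only at the later readings.

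**The power figures are for an unplanned analysis at assumed rates.** This stands, and they serve only to show scale. Assuming full recurrence within child softens the loss considerably at b = 0.20 and 0.30, which is why ranges are given.

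**Conclusion.** The point holds as a gap in how local reactions are recorded. The same skin is patched and cannulated, the inspections fall on both sides of the puncture, the only intensity named is an undated maximum, and cannulation is not offered as a cause. The recorded grades for erythema, ecchymosis, swelling and tenderness can therefore combine two sources.

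The consequence is inflated absolute rates and a weaker microneedle-versus-sham contrast. With a 30% device reaction rate and cannula reaction rates of 20% to 50%, the visible difference is 24 to 15 points instead of 30, and power is somewhere between 0.62 and 0.12 instead of 0.84. Both rates are assumptions, the test is illustrative, and the point lapses if the case report form already grades each time point. The efficacy endpoints are not affected. This is a cheap improvement, not a flaw that undermines the trial.

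**What to change.** In section 3.10.4 and the case report form:

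1. Record presence, size and grade of each solicited sign separately at the pre-cannulation inspection, the post-transfusion inspection and the phone call. Size matters because Appendix III starts grade 1 erythema, ecchymosis and swelling at 2.5 cm, while the needle array is 1 cm × 1 cm (3.9.1). A reaction confined to the array would fall below grade 1.
2. Add cannulation/transfusion as an attribution option beside microneedle and EMLA.
3. State the time point of each photograph.
4. In section 3.14, add a descriptive within-child table of microneedle against sham at each time point. Show the pre-cannulation table on its own as the reading free of cannula effects.
5. Keep and report the later readings, because delayed device reactions can appear only there.
6. Note with the table that the pre-cannulation reading comes at 15 minutes in one microneedle arm and at 30 minutes in the other three arms. Only microneedle with 1 FTU for 30 minutes matches the control on both cream amount and application time.

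The cost is a few more entries per visit and one descriptive table. Both inspections, the photographs and the phone call are already planned.
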